9.4.3 Follow-Up of Adverse Events

If any AEs are present when a subject completes 2 years post-implantation or ET, if earlier, or if a subject is withdrawn from the study, the subject will be re-evaluated within an appropriate period of time. At the investigator's discretion, minor AEs can be re-evaluated via telephone and documented. If the AE has still not resolved, additional follow-up will be performed as appropriate. Every effort should be made by the investigator or delegate to contact the subject until the AE has resolved or stabilized or the medical monitor and investigator agree that further follow-up is not necessary. This should be documented in the subject's medical records.

9.5 Reporting of Pregnancy

If a study participant becomes pregnant during study participation, basic information about the pregnancy will be recorded in the Pregnancy eCRF and submitted to CTI Safety. If there are complications during the pregnancy, the complications are recorded as AEs. The participant will be asked to report the outcome of the pregnancy and the site should submit the information to CTI Safety within 30 days after the outcome of the pregnancy. If there is a congenital anomaly in the infant, this will be recorded as a SAE in the data forms for the mother (i.e., the study participant).

Partner pregnancies do not need to be reported.

9.6 Data Monitoring Committee and Clinical Events Committee

9.6.1 Data Monitoring Committee

A Data Monitoring Committee (DMC) will be established to review safety on an ongoing basis and to provide recommendations about stopping, continuing or otherwise modifying the study. As part of their oversight of study conduct, the DMC will review the pattern of interventions and abandonments between treatment groups overall and by study site to assess whether the management of access complications is similar in the two treatment groups. The DMC will consist of individuals who are not directly involved in the conduct of the study. A separate charter will be established that will describe the roles and responsibilities of the DMC. Responsibilities of the DMC will include review of aggregate safety data from other studies in the HAV clinical development program.

9.6.2 Clinical Events Committee

A Clinical Events Committee (CEC) will be established to do the following:

- Prospectively provide to study sites a set of clinical guidelines for study conduit interventions and abandonment.
- Review study conduit interventions and abandonment in a blinded fashion to assess compliance with provided guidelines. Assessments by the CEC will be provided to the DMC by the CEC Coordinator (an employee of the CRO with no other study-related responsibilities).
- Adjudicate study conduit revisions to determine whether the original study conduit was still being used for dialysis.
- Adjudicate access-related infections using the Centers for Disease Control and Prevention (CDC) definitions for dialysis-associated infections ([CDC 2013](#)).

The outcome of these adjudications (i.e., those involving study conduit revisions and access-related infections) will be used as endpoints in the trial rather than the investigator determinations. All other study endpoints will be based on the clinical decisions of the investigators.

The CEC will consist of individuals who are not directly involved in the conduct of the study. A separate charter will be established that will describe the roles and responsibilities of the CEC.

9.7 New Information Affecting the Conduct of the Study

When new information becomes available for conducting the clinical study properly, Humacyte or designee will inform all investigators involved in the clinical study as well as the regulatory authorities. Investigators should inform the IRB/IEC of such information when needed.

10. STATISTICAL CONSIDERATIONS

This is a prospective, multicenter, multinational, open-label, randomized, two-arm, comparative study to compare the efficacy and safety of Humacyte's HAV with that of a ePTFE graft in subjects with ESRD. The primary objective of this study is to compare the Secondary Patency of the HAV and ePTFE grafts in these subjects. The key secondary objectives of this study are to compare the Primary Patency of the HAV and ePTFE grafts, and to compare the rate of access-related infections for the HAV and ePTFE grafts.

Additional details of data handling and planned statistics are provided in the Statistical Analysis Plan.

10.1 Randomization

Subjects will be randomized 1:1 to receive an HAV or an ePTFE graft. Randomization will be stratified by arm placement location (upper arm versus forearm placement) based on the Investigator's determination of where the study conduit should be located. Randomization by country will be used to ensure there is approximately the same count of subjects in each treatment group across each country. Prior to surgery the subject's eligibility will be reviewed by the Investigator and confirmed by the Medical Monitor. During surgery the Investigator will determine the implantation site (forearm versus upper arm) and confirm that the subject is not a candidate for creation of an autologous AV fistula. Randomization may occur once the arterial and venous exposures have been completed with confirmation of adequate arterial inflow and venous outflow.

10.2 Analysis Population

Efficacy

The primary analysis will be in the Intent-to-Treat (ITT) population with confirmatory analyses in the modified Intent-to-Treat (mITT) and Per Protocol (PP) populations.

The ITT population is defined as all randomized subjects (based on study conduit group assignment).

The mITT population is defined as all subjects in whom a study conduit has been implanted (based on actual conduit implanted).

The PP population is defined as all subjects in whom a study conduit has been implanted (based on actual conduit implanted) and in whom there were no major protocol deviations.

Safety

The safety analysis will be conducted using the safety population, which is defined as all subjects who receive study treatment, with the subject's treatment group based on the treatment that was received.

10.3 Efficacy Analysis

10.3.1 Censoring for Time to Event Analyses

- Subjects who have patent study conduits at the time of death, kidney transplant or withdrawal will be censored at that timepoint (additional efficacy analyses will consider death as an event-see [Section 10.3.4](#)).
- Subjects who are lost to follow-up will be censored at their last visit when it was known that the study conduit was patent.
- Subjects in whom a delayed decision is made to abandon the study conduit (e.g., delayed and then failed thrombectomy) will have the date of abandonment set as the date of the initial recognition of the thrombosis, not the date that a final decision was made.

These censoring rules will apply to all 'time to' analyses.

10.3.2 Primary Efficacy Analysis

The primary efficacy endpoint is the time to loss of Secondary Patency.

Study endpoints (see [Section 4.2](#)) will be determined by the clinical decisions of the investigators except for the following events that will be adjudicated by the CEC:

- Study conduit revisions to determine whether the original study conduit was still being used for dialysis.
- Access-related infections using the Centers for Disease Control and Prevention (CDC) definitions for dialysis-associated infections ([CDC 2013](#)).

The outcome of these adjudications will be used as endpoints in the trial rather than the investigator determinations.

The primary analysis will be a non-inferiority analysis, which will be conducted when all subjects are at least 18 months post-implantation.

The primary analysis will be in the ITT population with confirmatory analyses in the mITT and PP populations.

The following rules will apply to the ITT population:

- Subjects in whom the wrong study conduit was implanted (e.g., an HAV implanted in a subject randomized to an ePTFE graft) will be analyzed within their randomized group rather than in their 'implanted' group.
- Subjects in whom no study conduit was implanted will be considered as if abandoned on Day 0 and included in their randomized group.

The hazard ratio (HAV relative to ePTFE) will be estimated using a Cox proportional hazards regression model with treatment group and the randomization stratification variable as factors. Based on the estimated 18-month event-free rate in the ePTFE arm, the non-inferiority margin will be determined by the hazard ratio corresponding to a difference of 10 percentage points. If the lower limit of the two-sided 95% confidence interval for the hazard ratio is greater than the corresponding non-inferiority bound, then non-inferiority will be demonstrated.

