4.2 Study Endpoints

4.2.1 Primary Endpoint

Time to loss of Secondary Patency from implantation

- Defined as 'the interval from the time of access placement until access abandonment', i.e., patent with or without interventions ([Sidawy 2002](#)).
- "Abandonment" defined as no remaining segment of the study conduit is incorporated into the vascular access circuit used for dialysis (conversely, if some portion of the study conduit is still being used for dialysis it is not considered abandoned).

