10.5 Sample Size

The original sample size calculation was based on the following assumptions:

For the primary endpoint of time to loss of Secondary Patency, the assumed 12-month event-free rates in the ePTFE arm is 60%. Based on 1:1 randomization, a 16-month enrollment period, and a 12-month follow-up period, a total sample size of 350 subjects will provide:

- 90% power to demonstrate non-inferiority (non-inferiority margin=10%) if the 12-month event-free rate in the HAV arm is 66%
- 90% power to demonstrate superiority if the 12-month event-free rate in the HAV arm is 76%

For the key secondary endpoint of time to loss of Primary Patency, the assumed 6-month event-free rate in the ePTFE arm is 50%. Based on 1:1 randomization, a 16-month enrollment period, and a 12-month follow-up period, and under the assumption that the true 6-month event-free rate in the HAV arm is 55%, a total sample size of 350 subjects will provide greater than 90% power to demonstrate non-inferiority. If the true rate in the HAV arm is as low as 53%, then there will be greater than 80% power to demonstrate non-inferiority.

During the course of the study a high enrolling site (~10% of total subjects) early terminated all of their remaining subjects and withdrew from study participation. The majority of these subjects had not yet had an event that would contribute to the primary endpoint analysis. To mitigate the potential loss of study power from this unexpected situation, the decision was made to extend the follow-up period for the primary and secondary efficacy analyses from 12 months post-implant to 18 months post-implant.

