| 5.0
08AUG2018          | 6.1                | Changed 12 to 18 months after implantation for the primary efficacy endpoint

Changed "If the lower limit of the two-sided 95% confidence interval for the hazard ratio is greater than the corresponding non-inferiority bound" to " If the upper limit of the two-sided 95% confidence interval for the hazard ratio is less than the corresponding non-inferiority bound" | This was done to match the protocol and for clarification |

| Protocol Version # | SAP Section | Modification  | Description and Rationale   |
|---------------------------|--------------------|--|--|
| 5.0
08AUG2018          | 6.2                | 
Changed "Interventions required to achieve/maintain Secondary Patency." to "Interventions required that successfully achieved/maintained Secondary Patency."
 
Added language for checking overdispersion and using negative binomial regression if overdispersion is present
 
Added analysis for failed interventions.
 
Removed "Dichotomous data will be analyzed using Pearson's chi-square test to compare treatment groups."
 
Changed "1 year" to "18 months"
 | This was done for clarification, and to be consistent with the planned analysis for the study. |
| 5.0
08AUG2018          | 6.4                | Added more details for sub-group analysis.   | This was done for clarification, and to be consistent with the planned analysis for the study. |
| 5.0
08AUG2018          | 7.1                | Added an additional definition for exposure during the study period, and modified the original exposure definition.  | This was done for clarification, and to be consistent with the planned analysis for the study. |
| 5.0
08AUG2018          | 7.2                | Added details for TEAE derivation.   | This was done for clarification.   |
| 5.0
08AUG2018          | 7.2.5              | Added language for checking overdispersion and using negative binomial regression if overdispersion is present   | This was done for clarification, and to be consistent with the planned analysis for the study. |

| Protocol Version # | SAP Section | Modification  | Description and Rationale  |
|---------------------------|--------------------|--|---|
| Date               |                    |  |   |

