The hazard ratio (HAV relative to ePTFE graft) will be estimated using a Cox proportional hazards regression with treatment group and the surgical placement stratification variable as factors. Based on the estimated event-free rate in the ePTFE graft arm at the data cut-off using Kaplan-Meier method, the non-inferiority margin will be determined by the hazard ratio corresponding to a difference of 10 percentage points. Hazard Ratio (HAV to ePTFE) Margin = $\text{Log}(\text{ePTFE K-M estimated event free rate} - 0.1) / \text{Log}(\text{ePTFE K-M estimated event free rate})$ . For analyses conducted at 12 months, the hazard ratio will be calculated from the ePTFE K-M estimated event-free rate at 12 months. For analyses conducted at 18 months, the hazard ratio will be calculated from the ePTFE K-M estimated event-free rate at 18 months. Similarly, for analyses conducted at 24 months, the hazard ratio will be calculated from the ePTFE K-M estimated event-free rate at 24 months. If the upper limit of the two-sided 95% confidence interval for the hazard ratio is less than the corresponding non-inferiority margin hazard ratio, then non-inferiority will be demonstrated.

The primary analysis will be in the ITT analysis set. The analysis of the primary endpoints of interest will be repeated using the mITT and per-protocol analyses sets as confirmatory.

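### The protocol's primary non-inferiority rule is reversed: as written it passes HAV only when HAV is shown to be worse than the margin, and it contradicts the SAP

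*Protocol*

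**What the plan says.** The primary endpoint in Protocol 4.2.1 is "Time to loss of Secondary Patency from implantation", where loss means abandonment of the conduit.

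Protocol 10.3.2 fixes the direction of the comparison: "The hazard ratio (HAV relative to ePTFE) will be estimated using a Cox proportional hazards regression model". On the margin it says that "the non-inferiority margin will be determined by the hazard ratio corresponding to a difference of 10 percentage points". Non-inferiority is then declared on this condition: "If the lower limit of the two-sided 95% confidence interval for the hazard ratio is greater than the corresponding non-inferiority bound". The Protocol Summary (Primary Efficacy Analysis) carries the same sentence. Protocol 10.3.3 applies the primary analysis's approach and margin to the non-inferiority test of Primary Patency.

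SAP 6.1 uses the same direction. It defines the "Hazard Ratio (HAV to ePTFE) Margin" as the log of the ePTFE Kaplan-Meier event-free rate minus 0.1, divided by the log of that rate. Its condition is: "If the upper limit of the two-sided 95% confidence interval for the hazard ratio is less than the corresponding non-inferiority margin hazard ratio". SAP 6.1.1, item g, repeats that condition for the 24-month Cox analysis.

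The SAP revision table records that the SAP once had the lower-limit wording and that it was changed to the upper-limit wording. The stated reason is "This was done to match the protocol and for clarification".

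**The concern.** Loss of patency is an unfavourable event and HAV is in the numerator, so non-inferiority requires evidence that the hazard ratio is not too large. Such evidence comes from the upper confidence limit lying below a margin greater than 1. The protocol asks for the lower limit to lie above the bound, which is evidence that the hazard ratio is too large.

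This is the success criterion for the primary endpoint. Through the fixed sequence in Protocol 10.3.3 it also decides whether the key secondary efficacy tests are confirmatory, and the Primary Patency non-inferiority test inherits the wording. The access-related infection comparison lies outside that sequence and is not affected.

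The two current documents therefore state incompatible success criteria. No data set can satisfy both, and a reader with only the protocol would call a favourable result a failure.

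**Working it through.** **Inputs**

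- ePTFE event-free rate at 12 months: 60% (Protocol 10.5).
- HAV event-free rate at 12 months for non-inferiority: 66%, with stated power of 90% (Protocol 10.5).
- 350 subjects, 1:1, 16-month enrollment, 12-month follow-up (Protocol 10.5).
- Margin formula: SAP 6.1.
- Annual death rate of about 20%, with deaths censored (SAP 6.1). The sample-size section states no censoring rate, so its use here is an assumption.
- Exponential event times and uniform accrual: assumptions.

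**Step 1. Side of 1 on which the margin lies.** Margin = ln(S − 0.1)/ln(S), which exceeds 1 for any S between 0.1 and 1. At S = 0.60 it is ln(0.50)/ln(0.60) = 1.357. The documents give no 18-month planning rate. Extending 60% exponentially gives S = 0.60^1.5 = 0.465 and a margin of 1.316.

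**Step 2. The plan's own power figure.** True hazard ratio = ln(0.66)/ln(0.60) = 0.813. With hazard λ, accrual A = 16 and follow-up F = 12, the event probability is 1 − [exp(−λF) − exp(−λ(A+F))]/(λA). This gives 185.2 events over both arms. The standard error of the log hazard ratio is 2/√185.2 = 0.147.

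Power under the upper-limit rule = Φ[(ln 1.357 − ln 0.813)/0.147 − 1.96] = 93.6%. With 20% per year censored for death there are 157.9 events and power is 89.5%, which agrees with the stated 90%. Under the lower-limit rule the probability is Φ[(ln 0.813 − ln 1.357)/0.147 − 1.96] = 2.6 × 10⁻⁸. The stated power is attainable only with the upper-limit rule.

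**Step 3. Both rules over a range of true effects** (margin 1.357, 12-month follow-up, no censoring for death):

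| HAV 12-month rate | True hazard ratio | Events | Protocol rule declares non-inferiority | SAP rule declares non-inferiority |
|---|---|---|---|---|
| 76% | 0.537 | 162.5 | about 0 | >99.9% |
| 66% | 0.813 | 185.2 | 0.000003% | 93.6% |
| 60% | 1.000 | 197.7 | 0.002% | 57.4% |
| 50% | 1.357 (margin) | 216.7 | 2.5% | 2.5% |
| 40% | 1.794 | 233.4 | 56.8% | <0.01% |
| 35% | 2.055 | 240.9 | 89.6% | <0.01% |
| 30% | 2.357 | 247.7 | 99.1% | <0.01% |

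**Step 4. Two worked intervals.** The interval is exp(ln HR ± 1.96 × 2/√events).

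- An estimate of 0.813 with 185 events gives 0.61 to 1.09. It fails the protocol rule (0.61 is below 1.357) and passes the SAP rule (1.09 is below 1.357).
- An estimate of 2.0 with 239 events gives 1.55 to 2.58. It passes the protocol rule and fails the SAP rule.

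**Step 5. The current 18-month timing** (margin 1.316, no censoring for death). At a hazard ratio of 0.813 (219 events) the protocol rule succeeds with probability 1.7 × 10⁻⁸ and the SAP rule with 94.5%. At 2.0 (270 events) the figures are 93.1% and about 0. A simulation of 2,000 trials per scenario with 20% per year censored for death gave 0% against 90.3% at 0.813, and 87.3% against 0% at 2.0.

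**Step 6. Whether a bound below 1 would rescue the sentence.** It would not. With the inverse bound, 1/1.357 = 0.737, the lower-limit rule (12-month follow-up, no censoring for death) succeeds 9.9% of the time at 0.813 and 99.4% at 1.357. With ln(0.70)/ln(0.60) = 0.698, a difference of +10 points, the figures are 17.9% and 99.8%. Lower-limit wording suits only a ratio of ePTFE to HAV, which Protocol 10.3.2 rules out.

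**The case against.** The strongest reply is that the sponsor has already found and corrected this in the document that drives the analysis. The SAP revision table names the sentence and records the change. The current SAP states the right rule twice, with an explicit margin formula. Protocol section 10 leaves statistical detail to the SAP, and SAP section 4 provides for a SAP amendment when a principal feature of the protocol's analysis changes. The protocol's own 90% power shows what was meant. On this view it is a drafting slip, and the high false-success probabilities describe an analysis nobody will run.

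Much of that stands. The intent is clear, and the executed analysis is probably safe. The two rules also do not always disagree: both can fail on the same data. In the simulation at a true hazard ratio of 1.0 the SAP rule succeeded 48.4% of the time and the protocol rule never, so the verdict was the same in 51.6% of trials. At 1.316 the success rates were 2.7% and 1.9%, so the verdicts agreed in 95.4%. They are almost always opposite only when HAV is clearly better or clearly worse.

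The reply does not remove the conflict. Neither document says which prevails. SAP section 1 describes the SAP as giving details of analyses set by the protocol and commits the study to compliance with the protocol. The revision table's reason covers two changes in one row. It fits the move to 18 months, but not the reversal of the limit, because Protocol v5.0 still has the lower-limit rule.

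**Conclusion.** The concern holds. The primary success criterion in Protocol 10.3.2 and in the Protocol Summary is reversed, contradicts SAP 6.1 and 6.1.1 item g, and extends to the Primary Patency non-inferiority test through Protocol 10.3.3. Taken literally, it succeeds with probability of about 0 at the planned effect, where the SAP rule gives 89.5% to 93.6%. At a true hazard ratio of 2.0 with 18-month follow-up, it declares non-inferiority in 87% (with death censoring) to 93% (without) of trials.

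The direction of the error rests only on the protocol's definitions of endpoint, ratio and margin. The percentages rest on exponential event times, uniform accrual and the assumed censoring for death, and the 1.316 margin rests on extrapolating the 12-month rate. This must be fixed, because it is the trial's primary decision threshold. The practical risk is confined to the protocol text being followed, or cited against the result, in place of the SAP.

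**What to change.** In Protocol 10.3.2 and in the Primary Efficacy Analysis row of the Protocol Summary, replace the decision sentence with the SAP 6.1 rule: non-inferiority is shown if the upper limit of the two-sided 95% confidence interval for the hazard ratio (HAV/ePTFE) is below the margin hazard ratio. Add the margin formula and a statement that values above 1 favour ePTFE. Protocol 10.3.3 then inherits the correct rule without further change.

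In the SAP revision table, separate the two changes in the Section 6.1 row and describe the limit change as a correction of the protocol wording. If the protocol can no longer be amended, record in the clinical study report that the SAP 6.1 rule governs and that the protocol sentence is an error.

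The cost is one sentence in two places and one log entry. Sample size, conduct and data collection are unaffected.

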10.3.3 Key Secondary Efficacy Analyses

If the primary efficacy analysis demonstrates non-inferiority, the following key secondary analyses will be completed at the same timepoint in the ITT population using a fixed sequence testing procedure to control the overall level of significance. Thus, the results of a given key secondary analysis will be considered confirmatory only if the results of all previous tests are successful based on the use of a two-sided test at the alpha=0.05 level of significance. However, once a non-successful result is obtained, all subsequent results will be considered as exploratory rather than confirmatory. The key secondary analyses are as follows:

- Superiority analysis of the time to loss of Secondary Patency
- Non-inferiority analysis of the time to loss of Primary Patency
- Superiority analysis of the time to loss of Primary Patency

The non-inferiority analysis of time to loss of Primary Patency will be completed using the same statistical approach and non-inferiority margin as specified for the primary analysis.

The superiority analyses will be completed using the same statistical model as described for the corresponding non-inferiority analysis. The two arms will be compared using a two-sided test at the alpha=0.05 level of significance.

